5.3.4 Sensitivity Analyses for Primary Endpoints

The following sensitivity analyses for the primary endpoints are planned.

- To relax the assumption of the linearity in disease trajectory, a mixed model with repeated measures (MMRM) will be used. The response variable is change from baseline. The effects in the model will include baseline score, randomization factors, treatment group, visit, baseline score-by-visit interaction, and treatment-by-visit interaction. Visits will be treated as the repeated variable within a participant. Participant, treatment, and visit will be treated as class variables. An unstructured variance-covariance structure will be applied to model the within-participant errors; in the case of non-convergence, compound symmetry will be used. If non-convergence still exists, data from Year 8 (longest duration in the trial based on enrollment) will be removed, likely caused by a small number of datapoints at Year 8 due to the common-close study design. If non-convergence still exists, visit data will be removed in reverse chronological order until a convergence (either by unstructured or compound symmetry assumption, with unstructured always being tested first) is reached.

For instances where the score is assessed outside of the visit window described in the protocol, it will be mapped to the closest scheduled visit as described in the schedule of activities in Appendices A-1 through A-4 of the protocol.

Baseline score is defined as the last non-missing score on or before the first study drug exposure. After the mapping, if multiple scores exist at a visit, the score closest to the scheduled visit date is chosen in the MMRM analysis.

The difference between the crenezumab group and the placebo group in the least squares (LS) mean change from baseline will be estimated at each timepoint.

The 95% CIs and p-values for LS mean treatment difference will be presented.

The MMRM LS mean plot with standard errors (SEs) will be made to visually examine the linearity of the disease trajectory.

- To quantitatively examine the impact of the linearity assumption and the assumption of the variance decomposition in the RCRM, the robust variance estimator (Huber 1967; White 1982) will be used in the RCRM to re-calculate the SEs and; therefore, CIs and p-values in the primary analysis model
- Analysis assuming participants who *discontinue* from *crenezumab treatment* will lose the treatment effect instantaneously.
Immediately after a participant *discontinues in the first occurrence* from the *crenezumab treatment*, the population-level annualized rate of change will be assumed to be the same as the population-level annualized rate of change in the placebo arm. This approach will likely yield a conservative estimate of the treatment effect. In particular, the model is written as:

$$Y_{ij} = \alpha + (\text{Randomization Factors})_i + u_{0i} + (\beta + u_{1i})t_{ij} + \left(\beta_x \left(t_{ij} I_{t_{ij} \leq t_{i,discon}} + t_{DROP} I_{t_{ij} > t_{i,discon}} \right) \right) I_{x,i} + \epsilon_{ij}$$

where $t_{i,DROP}$ represents the time of *the first occurrence of discontinuation from the crenuzumab treatment* for participant i , and $I_{t_{ij} \leq t_{i,discon}}$ and $I_{t_{ij} > t_{i,discon}}$ are indicator variables similarly defined previously in this document. If a participant has not discontinued from the crenuzumab treatment during Study Period A, then $t_{i,discon}$ is defined as an arbitrarily large number (e.g., 100 with “year” as the unit). The 95% CIs and p-values for estimates in β_x will be presented.

- Analysis using control-based mean imputation
The underlying assumption of this sensitivity analysis is that the missing value mean from the crenuzumab arm is the same or worse than the estimated overall mean from the placebo arm. Consequently, this approach yields a conservative treatment effect estimate in crenuzumab. The details of this approach can be found in Mehrotra et al. (2017). The model setup and more statistical details can be found in [Appendix 3](#).
- Analysis using hypothetical strategy for all intercurrent events, except for the dosing regimen change. The intercurrent events and the handling strategy in this analysis is defined as follows:
 - Events that lead to treatment withdrawal due to an adverse event.
A hypothetical strategy where all values will be censored after the first occurrence of the intercurrent event.
 - Death: A hypothetical strategy where all values will be censored after the occurrence of the intercurrent event.
 - Pregnancy that leads to treatment withdrawal. A hypothetical strategy will be applied where all values will be censored after the occurrence of the intercurrent event.

- Resumption of dosing after treatment discontinuation post-protocol amendment, v8. A hypothetical strategy where all values will be censored after 1 day before the first occurrence of the intercurrent event.
- Dose change from SC to IV administration. A treatment policy strategy will be applied where all observed values will be used regardless of the occurrence of the intercurrent event.
- Events that lead to treatment interruption or withdrawal due to COVID-19 diagnosis. A hypothetical strategy where all values will be censored after the first occurrence of the intercurrent event.
- *Concurrent use of protocol-defined prohibited medications that can potentially impact cognition (e.g., anti-psychotics, anticonvulsants, benzodiazepines, etc.). A hypothetical strategy will be applied where all values will be censored from the start date of the occurrence of the intercurrent event to 2 days after the occurrence of the intercurrent event.*

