5.3.3 Main Analytical Approach for Primary Endpoint Family

The primary analysis on both primary endpoints will be performed using a RCRM (Richeldi et al. 2014; Flaherty et al. 2019; Hu et al. 2021) with a missing at random (MAR) assumption. This model will include all observations, including baseline scores as the response variable. The RCRM will include the randomization stratification factors described in Section 5.3 as fixed effects with an intercept, and will include the categorical treatment groups as interaction terms with time; *stratification factor(s) may be removed from the model if there is risk of non-convergence or sparse strata (in case*

of non-convergence, stratification factors will be removed in the order of the smallest number of observations in any cell caused by that stratification factor).

Participant-level random intercept and random slope are also included in the model, where an unstructured covariance between the random intercept and random slope is assumed. The RCRM is constructed as follows:

$$Y_{ij} = \alpha + (\text{Randomization Factors})_i + u_{0i} + (\beta + \beta_x l_{x,i} + u_{1i}) t_{ij} + \varepsilon_{ij}$$

where Y_{ij} is the score for participant i at visit j ; t_{ij} is the duration in the unit of year after first drug intake for participant i at visit j ; $l_{x,i} = 1$ if participant i in a *PSEN1* E280A mutation carrier is in the crenezumab mITT group, and $l_{x,i} = 0$ if participant i is a *PSEN1* E280A mutation carrier is in the placebo mITT group; u_{0i} and u_{1i} are random intercept and random slope, respectively, for the i^{th} participant; ε_{ij} is the random error for the i^{th} participant at visit j . The crenezumab treatment effect on the rate of change is quantified by β_x ; the 95% CI and p-value for crenezumab treatment effect will be presented. The crenezumab treatment effect compared with the placebo group on the relative reduction (RR) scale is calculated as $-\beta_x/\beta \times 100\%$; its estimate will also be presented; its 95% CI using bootstrap approach will also be provided.

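### If the unstructured MMRM fails to converge, SAP 5.3.4 falls back on compound symmetry, which makes the nominal visit-wise intervals too narrow at late visits and too wide at early ones

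*SAP*

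**What the plan says.** The first sensitivity analysis in SAP Section 5.3.4 is an MMRM meant to relax the linearity assumed by the primary model. "The response variable is change from baseline", with terms for baseline score, randomization factors, treatment, visit, and the baseline-by-visit and treatment-by-visit interactions. The covariance rule has three steps:

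1. "An unstructured variance-covariance structure will be applied to model the within-participant errors".
2. If that fails, "in the case of non-convergence, compound symmetry will be used".
3. Only then: "If non-convergence still exists, data from Year 8 (longest duration in the trial based on enrollment) will be removed". After that, visits are dropped from the latest backwards until a fit converges, "either by unstructured or compound symmetry assumption, with unstructured always being tested first".

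The SAP puts the likely failure down to sparse data at Year 8 under the common-close design. It lists no other covariance structure. For output, "The 95% CIs and p-values for LS mean treatment difference will be presented", together with a plot of LS means and standard errors. The robust variance estimator in the next bullet is specified for the primary model (RCRM) only.

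On the primary model, Section 5.3.3 says: "Participant-level random intercept and random slope are also included in the model", and "an unstructured covariance between the random intercept and random slope is assumed".

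**The concern.** With a random slope, participants drift apart as time passes, so change from baseline varies more at Year 7 than at Week 24. Compound symmetry cannot represent this. It pools small early variances with large late ones and applies the result everywhere, so late standard errors come out too small and early ones too large.

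The order of the steps adds to this. The SAP blames sparse Year 8 data, yet it changes the covariance for every visit before it removes those data. Compound symmetry has two parameters and seldom fails, so the Year 8 step, and the unstructured refit it would allow, would seldom be reached.

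At stake are the visit-wise intervals and p-values of this sensitivity analysis. Late visits, where a difference in slopes would be largest, are the ones that would look more precise than they are.

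**Working it through.** **Inputs.** SD of Week 260 change equal to 65% of the placebo mean decline, and 25% dropout (SAP Section 3). 84 carriers per arm (the SAP Appendix 2 simulation that mimics this study). At least 5 years of treatment with a common close (protocol Section 3.2), and a longest duration in Year 8 (SAP Section 5.3.4). The split of the change variance between slopes and residual error is in neither document, so it is assumed and varied from 0% to 75%.

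**The plan's own figure.** The documents give none for the MMRM. The SD input can be checked against the stated power. With 100 × 0.75 = 75 evaluable per arm and effect size 0.30/0.65 = 0.4615, 0.4615 × √(75/2) − 1.96 = 0.866, which gives 80.7% power (noncentral t: 80.2%). The stated figure of at least 80% is reproduced.

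**Number of covariance parameters.** The protocol flowcharts schedule the composite at Weeks 12, 24, 52, 76 and 104 and at 12 visits from Week 128 to Week 416: 17 post-baseline visits, or 16 for the FCSRT, which is not given at Week 12. Unstructured needs 17 × 18/2 = 153 or 16 × 17/2 = 136 parameters, for about 2 × 84 = 168 carriers, few of them at the latest visits.

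**Variance of change.** In the primary model the random intercept cancels from change, leaving Var(t) = σ₁²t² + 2σₑ². If slopes supply a share f of the Week 260 variance, then relative to Week 260 (before baseline adjustment)

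V(week) = f × (week/260)² + (1 − f).

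Here (24/260)² = 0.0085 and (388/260)² = 2.227.

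| f | Week 24 | Week 388 | Ratio |
|---|---|---|---|
| 0% | 1.00 | 1.00 | 1.0 |
| 25% | 0.752 | 1.307 | 1.7 |
| 50% | 0.504 | 1.613 | 3.2 |
| 75% | 0.256 | 1.920 | 7.5 |

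Compound symmetry forces this ratio to 1, which is right only when f = 0.

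**Simulation under no treatment effect.** 800 runs per scenario; data from the random-intercept, random-slope model; visits Week 24 to Week 388 (Week 416 was left out); common close at about 5 to 8 years; 25% dropout by Year 5. The fit was the SAP's MMRM with four binary covariates for the randomization factors, by REML with compound symmetry and model-based standard errors. Entries are type I error at nominal 5%, with the ratio of the compound-symmetry standard error to the true one in brackets.

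| Week (mean n) | f = 0% | 25% | 50% | 75% |
|---|---|---|---|---|
| 24 (164) | 5.1% (0.99) | 2.9% (1.09) | 0.9% (1.25) | 0.1% (1.62) |
| 260 (126) | 4.6% (1.03) | 7.1% (0.95) | 8.0% (0.89) | 10.7% (0.82) |
| 312 (83) | 5.8% (0.99) | 7.9% (0.91) | 10.7% (0.83) | 14.5% (0.74) |
| 364 (45) | 5.8% (0.98) | 8.5% (0.84) | 13.9% (0.73) | 22.4% (0.63) |
| 388 (28) | 3.7% (1.02) | 10.5% (0.82) | 15.9% (0.69) | 23.3% (0.58) |

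The Monte Carlo standard error is about 0.8 points at 5%. As a hand check, a standard error wrong by a factor r gives error 2 × [1 − Φ(1.96r)]; r = 0.89 gives 8.1%, against 8.0% simulated. Changing the baseline reliability to 0.5 or 0.85 at f = 50% barely moves the results (Week 260: 8.7% and 8.3%; Week 388: 15.6% and 15.2%).

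A second, separately built simulation (300 runs, same arm size, follow-up and dropout) gave 6–14% at Week 260, 9–25% at Week 388 and 0–1.3% at Week 24 for f = 25–75%, and about 5% with no slope variance. The wider ranges are the ones quoted in the conclusion.

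**Remedies tested.** In the 800-run simulation at f = 50%:

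| Week | Compound symmetry | Same fit, sandwich SE | True covariance |
|---|---|---|---|
| 260 | 8.0% | 5.0% | 3.9% |
| 312 | 10.7% | 4.6% | 3.7% |
| 364 | 13.9% | 5.6% | 4.4% |
| 388 | 15.9% | 7.9% | 5.1% |

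In the second simulation, sandwich errors on the compound-symmetry fit gave 4–7% at Weeks 260 to 364 and 8–11% at Week 388.

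**The case against.** The strongest reply is about reach. A reader might infer that the trial's type I error is inflated. The documents do not support that: success rests on the two RCRM tests at 0.04 and 0.01 and the graph-based procedure (SAP Sections 2 and 3.1). The MMRM has no decision rule, and its p-values, over up to 17 visits and two endpoints without multiplicity adjustment, are already nominal. This stands in full.

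A reader might also infer that the only check on linearity is lost. It is not. Section 5.3.4 also re-estimates the RCRM with robust variance, and Section 5.3.5 adds a quadratic RCRM. For linearity, the MMRM's stated use is a visual look at the LS means, and nothing here shows those means to be distorted; the error bars are what go wrong.

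A third tempting step is to call the fallback likely. A parameter count makes failure plausible, and the SAP itself provides for it, but no unstructured fit was attempted and no failure rate estimated. Every error rate above is conditional on that failure.

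Finally, the size depends on an assumed slope share, and the largest figures come from a visit with about 28 participants. That too stands, which is why a range including 0% is shown. It does not remove the point: at Week 260, which all participants are designed to reach, error is still above nominal for every non-zero share tried.

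**Conclusion.** The point holds as a defect in a stated fallback rule, not as a threat to the primary result. If the unstructured MMRM fails and slopes vary between participants, as the primary model allows, compound symmetry with model-based standard errors gives misleading visit-wise intervals and p-values. For assumed slope shares of 25–75%, type I error at nominal 5% is about 6–14% at Week 260 and 9–25% at Week 388, while early visits are conservative. With no slope variance there is no inflation.

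The direction follows from the SAP's own two models. The size rests on the assumed share, a linear random-slope process, 84 carriers per arm, 25% dropout and a common close at 5 to 8 years. Late visits would be falsely significant more often than stated; nothing supports saying that they will be. The sequence deserves changing because it is a written rule that would yield wrong reported intervals, and the repair is cheap.

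**What to change.** Reword the MMRM fallback in SAP Section 5.3.4 to this order:

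1. If unstructured fails, remove the Year 8 visits, naming the weeks meant, and refit unstructured.
2. If it still fails, use a prespecified structure whose variance can change with time. Heterogeneous Toeplitz, heterogeneous first-order autoregressive, or the primary model's random intercept and slope would all serve; which one is a matter of preference, but it should be named in advance.
3. Keep compound symmetry only as the last resort, so that the sequence has an end point.
4. Use robust (sandwich) standard errors with any structured fit.

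The cost is SAP wording and a few lines of code. There are two downsides. The Year 8 estimates are lost in the step 1 refit. Sandwich standard errors also stay somewhat liberal where few participants remain: on the compound-symmetry fit, about 8–11% at Week 388. That is why the structure should change as well as the standard errors.

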4.5.6 Early Termination Visit

Participants who discontinue from blinded treatment prior to completion of Study Period A (early treatment discontinuation) will be asked to stay in the study for continued safety and efficacy assessments at selected evaluation visits following completion of an ET visit (see study flowchart in [Appendix 1](#), [Appendix 2](#), [Appendix 3](#), and [Appendix 4](#)). Participants who discontinue from the study (ET), or who discontinue from blinded treatment and elect to no longer remain in the study, will be asked to return to the clinic for an ET visit (see the study flowchart in [Appendix 2](#) for participants receiving SC study drug and [Appendix 4](#) for participants receiving IV study drug). The ET visit should be 4 weeks from last dose. In addition, a final safety follow-up visit

should be completed 16 weeks after last dose to ensure adequate washout of study drug but may be scheduled sooner if needed.

Please see the study flowchart provided in [Appendix 2](#) or [Appendix 4](#) for assessments to be performed at the study completion/ET visit.

Participants that are study drug non-compliant may be withdrawn from study treatment. As standard guidance, this refers to the following: Participant misses more than 2 doses within a single, 6-month period; a one-time exception of 3 missed doses within a 6-month period will be allowed. In rare circumstances (e.g., hospitalization), the Medical Monitor has the discretion to allow additional missed doses.

In order to maximize the opportunity for all active trial participants to receive the higher dose (60 mg/kg IV) of study drug, participants who have withdrawn from study treatment *in Study Period A*, but remain in the study for safety and efficacy assessments will be permitted a one-time opportunity to return to the study and to receive the higher IV dose, provided they did not discontinue treatment due to an adverse event related to study drug, the investigator judges it is safe to restart study drug, and the participant consents to receive IV administration of study drug going forward. If the participant has not completed a complex visit within 6 months of restarting study drug, a complex visit should be completed prior to reinitiating study drug. The investigator may also order unscheduled laboratory assessments as necessary to ensure safety and appropriateness to resume study drug.

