4.10.8 Determination of Sample Size

This study will enroll up to 300 participants: up to 200 participants will be enrolled in the carrier cohort and up to 100 participants will be enrolled in the non-carrier cohort.

Participants in the carrier cohort will be randomized in a 1:1 randomization ratio of active to placebo participants. The study was originally powered to compare the mean change from baseline over 260 weeks in the API ADAD Composite Cognitive Test total score between the crenezumab group and the placebo. Assuming a 25% dropout rate, two-sided testing at an overall 0.05 level, a placebo group CV of 65% for the Week 260 change scores ($=100\% \times$ standard deviation of placebo participant change scores/mean of placebo participant change scores) and 100 participants per arm, the study will have at least 80% power to detect a true effect of 30% reduction of the mean decline in the placebo group.

Participants in the non-carrier cohort will all receive placebo and will be included in the study in order to maintain the genotype blind.

The study was originally powered based on the API ADAD Composite Cognitive Test Battery total score. However, due to concerns about learning effects and general lack of sensitivity to change in a cognitively normal population, before study unblinding, the Sponsor performed a blinded power analysis on the original primary endpoint API ADAD Composite Cognitive Test Battery Total Score and the secondary clinical endpoints. The Sponsor decided to promote the FCSRT Cueing Index from a secondary endpoint to part of a primary endpoint family (along with the API ADAD Composite) due to its favorable statistical properties and clinical relevance as a sensitive measure of episodic memory dysfunction—the hallmark of emerging symptomatic AD and the most commonly observed, early, and consistent neuropsychological marker of AD (Tounsi et al. 1999; Bateman et al. 2012; Caselli et al. 2020) In the SAP, the Sponsor will provide details of the blinded power analysis along with the evidence of type I error control.

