3. SAMPLE SIZE DETERMINATION

This study will enroll up to 300 participants: up to 200 participants will be enrolled in the carrier cohort and up to 100 participants will be enrolled in the non-carrier cohort. Participants in the carrier cohort will be randomized in a 1:1 randomization ratio to active treatment or placebo. The study was initially powered to compare the mean change from baseline over 260 weeks in the API ADAD Composite Cognitive Test total score between the active treatment group and the placebo group. Assuming a 25% dropout rate with use of two-sided testing at the overall 0.05 level, a placebo group coefficient of variation of 65% for the Week 260 change scores ($= 100\% \times$ standard deviation of

[figure not shown]
placebo participant change scores/mean of placebo participant change scores) and 100 participants per arm, the study will have at least 80% power to detect a true effect of 30% reduction of the mean decline in the API ADAD Composite Cognitive Test total score in the placebo group using a t-test. Participants in the non-carrier cohort will all receive placebo and will be included in the study in order to maintain the genotype blind.

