5.3.5 Supplementary Analyses for Primary Endpoints

The following supplementary analyses will be performed for the primary endpoints to provide further understanding of the treatment effect.

- Analysis investigating efficacy in SC crenezumab versus efficacy in IV crenezumab: In this analysis, the treatment effect will be assumed to be different between the 2 administration periods. This analysis intends to gain insight on the impact of dose on the treatment effect. Since the IV dose is approximately 4-fold higher than the SC dose, we can use the administration method as a proxy for the dose. In this analysis, the change in administration method is assumed to change the population-level outcome trajectory for participants in the placebo group. For participants in the crenezumab group, the population-level outcome trajectory will also change once an administration method occurs. Furthermore, the switch can only go from SC to IV. In particular, the statistical model is constructed as:

$$Y_{ij} = \alpha + (\text{Randomization Factors})_i + u_{0i} + (\beta + u_{1i})t_{ij} + \beta_p(t_{ij} - t_{i,s})(1 - I_{x,i})I_{t_{ij} > t_{i,s}} + \left((\beta_{SC,x}t_{ij})I_{t_{ij} \leq t_{i,s}} + (\beta_{IV,x}(t_{ij} - t_{i,s}) + \beta_{SC,x}t_{i,s})I_{t_{ij} > t_{i,s}} \right)I_{x,i} + \epsilon_{ij}.$$

In this model, $t_{i,s}$ denotes the switching time for participant i after baseline; if a participant never switched in Study Period A of the study, then $t_{i,s}$ is defined as an arbitrarily large number (e.g., 100 with “year” as the unit). The parameter β_p denotes the effect of the change in administration method for participants in the placebo group. The variables $I_{t_{ij} \leq t_{i,s}}$ and $I_{t_{ij} > t_{i,s}}$ are indicator variables similarly defined as $I_{x,i}$. The annualized treatment benefit of crenezumab by SC is quantified by $\beta_{SC,x}$; the annualized treatment benefit of crenezumab by IV is quantified by $\beta_{IV,x}$. For model simplicity, up to 1 switch is assumed. The 95% CIs and p-values for estimates in $\beta_{SC,x}$ and $\beta_{IV,x}$ will be presented. The point estimates for the SC and IV treatment effect in the RR scale will also be presented.

- Analysis on each component of the API ADAD Composite Cognitive Test total score

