To understand the treatment effect on each component of one of the primary endpoints (API ADAD Composite Cognitive Test total score), the same primary analysis model will be run on each component. The 95% CIs and p-values for the treatment effect estimator will be presented. A forest plot will be made.
- To explore whether decline accelerates or decelerates, a quadratic RCRM where leading t^2 terms (treatment and time 2 interaction terms and random quadratic term) are added to the primary analysis model. The covariance matrix of $\{u_{0i}, u_{1i}, u_{2i}\}$ is assumed to be unstructured and all random effect terms are assumed to be independent of the pure error term. Specifically, this model is written as:

$$Y_{ij} = \alpha + (\text{Randomization Factors})_i + u_{0i} + (\beta + \beta_x I_{x,i} + u_{1i})t_{ij} + (\theta + \theta_x I_{x,i} + u_{2i})t_{ij}^2 + \epsilon_{ij}.$$

All statistical inferences as in the primary analysis model along with the point estimates of θ_x and 95% CI will be presented.

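### SAP 5.3.4: the discontinuation sensitivity model breaks the slope in the crenezumab arm only, so non-linear decline common to both arms can appear as a drug effect, in either direction

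*SAP*

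**What the plan says.** SAP 5.3.4 describes an analysis in which the drug effect is lost at once on stopping crenezumab: after the first discontinuation, "the population-level annualized rate of change will be assumed to be the same as the population-level annualized rate of change in the placebo arm". It adds: "This approach will likely yield a conservative estimate of the treatment effect". A 95% CI and p-value for β_x will be presented.

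In the printed formula the whole discontinuation bracket is multiplied by the crenezumab indicator I_x. The formula and its legend use t_DROP, t_i,DROP and t_i,discon without defining each. The sensible reading is that all three mean the time of first discontinuation.

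Four other places bear on this:

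- **Off-drug data.** Under Protocol 4.5.6, participants who stop treatment "will be asked to stay in the study for continued safety and efficacy assessments". SAP 5.3.2 uses all observed values after withdrawal for an adverse event or pregnancy.
- **Shape of decline.** SAP 5.3.4 plans an MMRM to relax linearity. SAP 5.3.5 plans a further model: "To explore whether decline accelerates or decelerates, a quadratic RCRM".
- **Practice effects.** Protocol 4.10.8 explains the review of the primary endpoint as "due to concerns about learning effects and general lack of sensitivity to change in a cognitively normal population".
- **A break elsewhere.** In the SC versus IV model of SAP 5.3.5, "the change in administration method is assumed to change the population-level outcome trajectory for participants in the placebo group".

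**The concern.** A placebo participant who stops injections or infusions stays on one straight line. A crenezumab participant who stops is allowed a change of slope, and that change is read as loss of drug effect. Anything else that bends the trajectory over time has nowhere to go in the model except β_x.

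The analysis is meant to stress-test the primary result. If its null rejection rate depends on the shape of decline, it can appear to confirm a chance or borderline primary finding, or to contradict a sound one. Its description as likely conservative would lead readers to trust it.

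**Working it through.** **1. The plan's own power figure.** SAP section 3 gives "two-sided testing at the overall 0.05 level", "a placebo group coefficient of variation of 65% for the Week 260 change scores", 100 per arm, 25% dropout and a 30% reduction. Evaluable per arm: 100 × 0.75 = 75. Standardised effect: 0.30/0.65 = 0.4615. Noncentrality: 0.4615 × √(75/2) = 2.83. Power is 80.7%, agreeing with the stated 80% or more. The required number is 74 per arm, and 74/0.75 rounds up to 99 against the stated 100. These values set the scale of decline and its SD below.

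**2. What the formula estimates.** Reading t_DROP as t_i,discon, the drug term is β_x·min(t, t_discon)·I_x. The mean slopes are:

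| Arm | Before stopping | After stopping |
|---|---|---|
| Crenezumab | β + β_x | β |
| Placebo | β | β |

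So β_x is informed by the randomised slope contrast and by the before-minus-after contrast within crenezumab stoppers. A participant's random slope cancels from the second, which gives it real weight.

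**3. Hand example, no drug effect.** Let both arms follow −m[(1−k)t/5 + k(t/5)²], where m is the 5-year decline and k the quadratic share. Take k = 0.5, stopping at 2.5 years, follow-up to 5 years.

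- Decline before stopping: m(0.25 + 0.125) = 0.375m, or 0.15m per year.
- Decline after stopping: 0.625m, or 0.25m per year.
- Steepening: 0.10m per year, half the average slope of 0.20m.

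Placebo stoppers steepen identically, but the model can represent this only as β_x > 0. With k = −0.5 the two rates swap and the sign reverses.

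**4. Null simulation.** From the documents: 84 carriers per arm (SAP Appendix 2), 5 to 8 years of follow-up, visits roughly every 24-28 weeks, CV 0.65. Assumed:

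- the proportion stopping, 25% unless stated (borrowed from the dropout rate);
- the share of stoppers still assessed;
- residual error as a share of the Week 260 change variance;
- curvature k;
- stopping times uniform over most of the first 5 years, with the same process in both arms and no link to outcome.

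The fit was a REML random intercept and slope model, two-sided |z| > 1.96, without randomization factors. Percent rejecting, 800-1000 replicates per row (Monte Carlo SE at most about 1.8 points):

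| k | Stop drug | Stoppers assessed | Residual share | Primary RCRM | SAP discontinuation model | With shared post-stop slope |
|---|---|---|---|---|---|---|
| 0 | 25% | half | 0.3 | 6.6 | 4.9 | 5.4 |
| 0.25 | 25% | half | 0.3 | 5.6 | 9.9 | 5.4 |
| 0.5 | 25% | half | 0.3 | 5.5 | 21.1 | 4.8 |
| 1 | 25% | half | 0.3 | 4.9 | 43.2 | 5.3 |
| 0.5 | 25% | half | 0.6 | 5.2 | 9.5 | 5.2 |
| 1 | 25% | half | 0.6 | 5.1 | 16.8 | 5.8 |
| 0.5 | 25% | all | 0.6 | 5.6 | 15.9 | 5.1 |
| 1 | 25% | all | 0.6 | 5.0 | 38.8 | 5.9 |
| 0.5 | 25% | all | 0.3 | 5.4 | 48.1 | 5.0 |
| 1 | 25% | all | 0.3 | 5.9 | 83.5 | 5.0 |
| 0.5 | 10% | half | 0.3 | 5.8 | 9.0 | 4.9 |
| 0.5 | 25% | about 2% | 0.3 | 5.2 | 5.0 | 5.0 |
| −0.5 | 25% | half | 0.3 | 6.2 | 18.4 | 6.0 |

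With accelerating decline nearly all rejections favour crenezumab. In the rows with k above 0 and half or all stoppers assessed, the spurious benefit is about 4-29% of the placebo slope. In the k = −0.5 row only 0.4% favour crenezumab.

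A second set of runs (400-500 replicates, all stoppers assessed, residual share 0.3 unless stated) gave, for the SAP model:

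- k = 0.25: 16.4%; k = 0.5: 44.2%.
- k = 0.25 with 10% or 15% stopping: 6.8% and 8.5%; with residual share 0.6: 8.7%.
- Linear decline plus a shared practice gain of 0.25 or 0.5 SD: 9.2% and 31.0%.

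**The case against.** The case against is substantial, and most of it limits the claim.

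- **The inputs are not in the documents.** The 25% is a sample-size dropout rate, not a rate of stopping drug while staying in follow-up. Stoppers are asked to stay; no retention figure is given. This stands. With few stoppers, mild curvature or larger residual error the rate is about 7-10%, and with almost no retention it is 5%.
- **The documents state no direction of curvature.** SAP 5.3.5 is neutral between acceleration and deceleration. Protocol 4.10.8 mentions learning effects in choosing endpoints, not as a forecast of trajectory. This stands: the bias can run either way.
- **The SC versus IV model is a weak precedent.** Its placebo term applies to placebo only and is not subtracted from the IV effect, so it is no shared control. This stands; the point rests on the discontinuation formula alone.
- **Other analyses examine non-linearity and discontinuation.** The MMRM, its mean plot and the quadratic model would show marked curvature. Control-based imputation and the hypothetical-strategy analysis address dropout and intercurrent events. None alters this model or its p-value.
- **A shared post-stop slope changes the assumption.** The SAP has stoppers take the slope of the whole placebo arm; the remedy gives them the slope of placebo stoppers. This stands and should be stated in the SAP.

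A reader might infer that the trial's false-positive rate is inflated, that the error always favours crenezumab, or that a figure such as 44% is the rate to expect. The documents support none of these. Success and alpha rest on the primary RCRM through the graphical procedure, and that model stayed at 4.9-6.6% in the tabled runs.

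**Conclusion.** The model as printed does not isolate loss of drug effect at discontinuation. Part of β_x is an uncontrolled before/after contrast. If decline is non-linear in both arms and a material share of stoppers remain assessed, the null rejection rate of this one sensitivity analysis can rise well above 5%: about 10-45% across most assumptions tried, higher in extreme cases, and near 5% if decline is linear or almost no stoppers stay. Acceleration or early practice gain is counted as benefit, deceleration as harm, so the conservative description is not assured. The primary test and the 0.04/0.01 split stand. The size depends on stopping rate, retention, residual share and curvature, all assumed; the asymmetry itself is visible in the formula.

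**What to change.** In SAP 5.3.4:

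1. Define t_i,discon as first discontinuation of study drug in either arm, and use that one symbol in place of t_DROP and t_i,DROP.
2. Add β_d·(t_ij − t_i,discon)·I(t_ij > t_i,discon) for both arms, and keep β_x·min(t_ij, t_i,discon)·I_x.
3. State that crenezumab stoppers then revert to the slope of placebo stoppers rather than of the whole placebo arm.
4. Remove or qualify the description of the estimate as conservative.

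The shared term gave 4.8-6.0% rejection in all tabled scenarios, with bias of at most 0.6% of the placebo slope.

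A common non-linear time term is an alternative that keeps the stated assumption; a t² term gave 5.0-5.8% in the same scenarios. It protects less if stopping is related to decline: in one such scenario (100 replicates) it rejected in 28%, against 4% with the shared post-stop slope. At that size the simulation errors are about 4.5 and 2 points.

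The cost is SAP wording and one fixed effect. SAP 5.7.1 already tabulates treatment discontinuation by group. With a true 30% on-drug effect, linear decline and all stoppers assessed, power of this sensitivity model fell from 95.3% to 93.2%.
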